### **5.2.2 Timing of Dose Administration**

MK-8628 is to be administered orally with water in a fasted state, and as part of a BID regimen (twice daily, approximately 12 hours apart). Subjects should not have food for 1 hour before or 3 hours after study drug administration.

Dosing not performed at the same time ( $\pm 2h$ ) as on other days should be skipped. Subjects are to be instructed that if they vomit or omit their dose in that time frame, it is not to be replaced. Capsules must not be opened or chewed.

A treatment cycle is 21 days (3 weeks). The subsequent cycle will begin on day 22 or after recovery from any AEs to baseline or Grade < 2 associated with the previous cycle.

Subjects should receive study treatment within 3 days following treatment allocation.

Details of the exact dose and time of administration will be documented in a validated subject diary and reported in the electronic case report form (eCRF).

#### **5.2.2.1 Premedication**

No systematic premedication will be given at least during the first cycle. See section 5.5 for a list of allowed and prohibited medications.

### **5.2.3 Trial Blinding**

This is an open-label trial; therefore, the Sponsor, investigator and subject will know the treatment administered.

## **5.3 Randomization or Treatment Allocation**

Cohort management and treatment allocation will occur centrally using an interactive web response system (IWRS). Subjects will be allocated to treatment by non-random assignment based on the open dosing cohort and number of available slots.

### **5.4 Stratification**

No stratification based on age, sex or other characteristics will be used in this trial.

## 5.5 Concomitant Medications/Vaccinations (Allowed and Prohibited)

Medications or vaccinations specifically prohibited in the exclusion criteria are not allowed during the ongoing trial. If there is a clinical indication for any medication or vaccination specifically prohibited during the trial, discontinuation from trial therapy or vaccination may be required. The investigator should discuss any questions regarding this with the Sponsor Clinical Director. The final decision on any supportive therapy or vaccination rests with the investigator and/or the subject's primary physician. However, the decision to continue the subject on trial therapy or vaccination schedule requires the mutual agreement of the investigator, the Sponsor and the subject.

### 5.5.1 Medications

All treatments taken by subjects at study entry or within 4 weeks or 5 half-lives prior to initiating treatment (whichever is longer) or at any time during the study, in addition to the investigational product are considered concomitant medications and must be documented in the eCRF.

No premedication is planned.

#### Allowed

Listed below are allowed concomitant medications / therapy during the course of the trial:

1. Supportive treatment of symptoms/adverse events or standard treatment of concomitant conditions, notably transfusion support and antibiotics or bisphosphonates will be given as medically indicated and reported in the eCRF.
2. Chemotherapy, hormone therapy or any other anticancer therapy or surgical intervention resection performed  $\geq$  3 weeks prior to study start ( $\geq$  6 weeks for nitrosoureas or mitomycin C) or  $\geq$  3 half-lives for monoclonal antibodies or  $\geq$  5 half-lives for other non-cytotoxic agents (whichever is longer).
3. Subjects on anticoagulant or antiaggregant (including low-dose aspirin) therapy at screening for concomitant medical conditions should be evaluated in coordination with their cardiologist for the benefit/risk ratio of continuing their anticoagulant or antiaggregant therapy during the study due to the potential increased risk of bleeding in the event of occurrence of severe thrombocytopenia. Blood cell count should be performed more frequently in such subjects, at least weekly throughout study, and more often in cases of grade 2 to 3 thrombocytopenia.

### **Prohibited**

Listed below are specific restrictions for concomitant medications / therapy during the course of the trial:

1. Concurrent treatment with any investigational drug or anticancer (antineoplastic) therapy, including the following: chemotherapy, immunotherapy, hormone therapy, or biological therapies.

*(The only exception is hydroxyurea given to control hyperleukocytosis that can be continued until 48 hours before MK-8268 treatment initiation, but must be stopped at that time. Furthermore, should a rapidly increasing white blood cell count occur during the first cycle of MK-8268 treatment, hydroxyurea should not be given earlier than day cycle 1 / day 3, nor beyond day 43 (cycle 3 / day 1), and for the shortest period possible as clinically indicated to control hyperleukocytosis and maintain the subject on study. On day 43 (cycle 3 / day 1), the decision to start MK-8268 for cycle 3 will be made by the investigator according to the subject's anticipated benefit. If hydroxyurea has to be resumed during cycle 3, this will be considered as MK-8268 treatment failure, and the subject will be withdrawn from the study)*

2. Corticosteroids (except chronic treatment with  $\leq$  4.0 to 6.0 mg / day of methylprednisolone or equivalent dose of other corticosteroids).
3. Prophylactic antiemetic drugs or other drugs given with a prophylactic intent in the first cycle (unless the Early Phase Safety Teleconferences Meeting decides to deliver systematic premedication).
4. Strong inducers, strong inhibitors, and sensitive / narrow therapeutic range substrates of the P450 cytochrome enzymes CYP3A4 and CYP2A6 (see Section 12.9) are prohibited. Moderate inducers and moderate inhibitors of these cytochrome enzymes should be used with caution. Since this list is not comprehensive, the investigator should use his/her medical judgment when a subject presents with a medication not on the list or call the Sponsor Clinical Director for clarification.

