#### 4.2.3.3.2 Exploratory Efficacy Endpoints

Exploratory efficacy endpoints include PFS, defined as the time from allocation to the first documented disease progression according to Response Evaluation Criteria in AML or DLBCL (see Section 7.1.2.7.1 and 7.1.2.7.2), or death due to any cause, whichever occurs first, and OS.

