#### 5.1.2 Subject Inclusion Criteria

In order to be eligible for participation in this trial, the subject must:

1. Be willing and able to provide written informed consent for the trial. Study entry is defined as the date that subject provides written informed consent. The subject may also provide consent for Future Biomedical Research. However, the subject may participate in the main trial without participating in Future Biomedical research.
2. Be  $\geq 18$  years of age on the day of providing written informed consent.
3. Have an ECOG performance status score of  $\leq 1$ .
4. Have an interval of  $\geq 3$  weeks since chemotherapy ( $\geq 6$  weeks for nitrosoureas or mitomycin C), immunotherapy, hormone therapy or any other anticancer therapy (including investigational) or surgical intervention resection, or  $\geq 3$  half-lives for monoclonal antibodies, or  $\geq 5$  half-lives for other non-cytotoxic agents (whichever is longer).
5. Female subjects of childbearing potential must have a negative urine or serum pregnancy test within 72 hours prior to receiving the first dose of study medication. If the urine test is positive or cannot be confirmed as negative, a serum pregnancy test will be required.
6. Female subjects of childbearing potential should be willing to use an adequate method of contraception as outlined in section 5.7.3 - Contraception, for the course of the study through 90 days after the last dose of study medication. Note: Abstinence is acceptable if this is the usual lifestyle and preferred contraception for the subject.
7. Male subjects of childbearing potential 5.7.3 – Contraception, starting with the first dose of trial treatment through 90 days after the last dose of study medication. Note: Abstinence is acceptable if this is the usual lifestyle and preferred contraception for the subject
8. Demonstrate adequate organ function as defined in [Table 1](#) below. All screening labs should be performed within 7 days of treatment initiation.

Table 1 Adequate Organ Function Laboratory Values

System	Laboratory Value
Hematological	
Absolute neutrophil count (ANC)	AML Subjects = No Limit DLBCL Subjects = $\geq 1.0 \times 10^9/L$
Platelets	AML Subjects = No Limit DLBCL Subjects = $\geq 150 \times 10^9/L$ (4 weeks without transfusion)
Hemoglobin	AML Subjects = No Limit DLBCL Subjects = $\geq 8.0 \text{ g/dL}$ (4 weeks without transfusion)
Renal	

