- b. MK-8628 is to be administered orally with water in a fasted state, and as part of a BID regimen (twice daily, approximately 12 hours apart). Subjects should not have food for 1 hour before or 3 hours after study drug administration. Dosing not performed at the same time ( $\pm 2$ h) as on other days should be skipped. Subjects are to be instructed that if they vomit or omit their dose in that time frame, it is not to be replaced.
- c. Collected at the following time points on day 1 of cycle 1: pre-dose, 1 hour post-dose, 2 hours post-dose.
- d. Collected prior to the subject dosing (pre-dose) on that day.
- e. Collected prior to the subject dosing (pre-dose) on day 1 of every odd treatment cycle (every 6 weeks) after cycle 3 day 1.
- f. AML tumor response assessments will be completed through the analysis of bone marrow aspiration samples and bone marrow biopsy samples (if necessary). See Section 7.1.2.7.1. Bone marrow analysis is required at screening, cycle 2 day 1, and cycle 3 day. Tumor response assessments will be conducted on day 1 of every cycle beyond cycle 3 through hematological analysis of peripheral blood. Evidence of response in peripheral blood may be confirmed by further bone marrow assessments as displayed in the tumor response criteria. The timing of tumor response assessments should follow calendar days and should not be adjusted for delays in cycle starts.
- g. DLBCL tumor response assessments will be completed through PET-CT and CT imaging analysis. See Section 7.1.2.7.2. The timing of tumor response assessments should follow calendar days and should not be adjusted for delays in cycle starts. The same imaging technique should be used in a subject throughout the trial. Routine imaging assessments (or bone marrow biopsy) performed outside of the scope of this study will be acceptable to complete the response criteria for DLBCL at screening, if performed  $\leq 4$  weeks prior to study entry. Assessment of lymphoma B symptoms should occur with each lymphoma disease response assessment.

- h. In subjects with an unconfirmed PD assessment, a radiological assessment should be performed at the time of treatment discontinuation. If previous scan was obtained within 4 weeks prior to the date of discontinuation, then a repeat scan at treatment discontinuation isn't mandatory. However, imaging should occur at any time where there is clinical suspicion of progression.

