### 8.4.2 Efficacy/Pharmacokinetics/Pharmacodynamics Endpoints

Secondary efficacy endpoints are presented below:

**Objective Response Rate (ORR):** is defined as the percentage of subjects who have achieved confirmed complete response (CR) or partial response (PR) according to specified response criteria for each tumor type (AML or DLBCL) by the investigator review.

**Duration of Response (DOR):** is defined as the time interval between the date of the first confirmed response (CR/PR) (the response prior to confirmation) and the date of first documented disease progression based upon specified response criteria for each tumor type (AML or DLBCL) by the investigator review.

**Disease Control Rate (DCR):** is defined as the percentage of subjects who have achieved stable disease or confirmed complete response (CR) or confirmed partial response (PR) according to Response Evaluation Criteria in AML or DLBCL (see Section 7.1.2.7.1 and 7.1.2.7.2) by the investigator review. Subjects with missing response will be considered not to have achieved disease control.

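### The AML efficacy definitions have no rule for permitted hydroxyurea, and the hydroxyurea treatment failure declared for Cycle 3 is not an event in any endpoint

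*Combined protocol and SAP*

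**What the plan says.** - **Section 5.5.1, Prohibited, item 1.** Hydroxyurea is the only exception to the ban on concurrent anticancer therapy. The trigger is "should a rapidly increasing white blood cell count occur during the first cycle of MK-8268 treatment" (the compound number is transposed there; I read it as MK-8628). The window is "hydroxyurea should not be given earlier than day cycle 1 / day 3, nor beyond day 43 (cycle 3 / day 1"), and use is "for the shortest period possible as clinically indicated to control hyperleukocytosis and maintain the subject on study". Before treatment, hydroxyurea may continue until 48 hours before the first dose.
- **Same item, consequence.** "If hydroxyurea has to be resumed during cycle 3, this will be considered as MK-8268 treatment failure", and the subject is withdrawn.
- **Section 6.0, footnote f.** "Bone marrow analysis is required at screening, cycle 2 day 1, and cycle 3 day"; the last day number is missing there, and Section 7.1.2.7.1 gives it as Day 1. After Cycle 3, AML response is assessed in peripheral blood, with marrow optional.
- **Section 8.4.2.** ORR counts confirmed CR or PR. DCR "is defined as the percentage of subjects who have achieved stable disease or confirmed complete response (CR") or confirmed PR, and only a missing response is set to failure. DOR ends at first documented progression; Section 4.2.3.3.1 adds death.
- **Section 4.2.3.3.2.** PFS ends at "the first documented disease progression according to Response Evaluation Criteria in AML or DLBCL", or at death. Section 8.6 defers methods for exploratory endpoints to a supplemental SAP.
- **Section 12.4, Table 13 (AML criteria).** Treatment failure means resistant disease or one of two death categories. Hydroxyurea resumption is not listed, and there is no stable-disease category.
- **Section 5.1.2, criterion 4.** At least 3 weeks must have passed since chemotherapy, "immunotherapy, hormone therapy or any other anticancer therapy (including investigational) or surgical intervention resection". Section 5.5.1, Allowed, item 2 repeats the interval.

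**The concern.** Antitumor activity of MK-8628 as a single agent is a secondary objective (Section 3.2), and an early efficacy signal is one of the supportive inputs to the RP2D (Section 5.2.1.4). Two things can blur that signal in the AML cohort.

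First, both scheduled post-baseline marrows can be read while a second cytoreductive drug is being given, and nothing in the endpoint definitions separates those readings from the rest.

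Second, the protocol names an outcome that it regards as failure of the study drug, and the endpoint definitions do not use it. How such a subject enters DOR or PFS is left to whether progression happens to be documented.

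The expected signal is small. Section 4.1.1.3 reports 2 CR and 1 CR with incomplete marrow recovery among 75 subjects with acute leukemia in MK-8628-001, that is 3/75 = 4.0%. Against such a rate, one or two ambiguous subjects matter.

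**Working it through.** **1. Timing.** Cycles last 21 days (Section 5.2.2), so Day 1 of cycle k is study day 1 + 21(k − 1).
- Cycle 2 Day 1 = 1 + 21 = Day 22; with ±3 days, Days 19–25.
- Cycle 3 Day 1 = 1 + 42 = Day 43; with ±3 days, Days 40–46.
- Hydroxyurea window: Days 3–43, or 43 − 3 + 1 = 41 days.

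The first marrow lies wholly inside the window. The second lies inside it up to Day 43.

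**2. Does an existing rule close the gap?**
- Section 8.4.2 asks for confirmed response but sets no confirmation interval, and the CR footnote to Table 13 requires no minimum duration. Both marrows can fall under hydroxyurea.
- The efficacy population (Section 8.5.2) is everyone with at least one dose, with no condition on hydroxyurea.
- DCR counts stable disease, but Table 13 does not define it for AML. A phase 1 subject with persistent leukemia and no CR, CRi or PR is there classed as resistant disease, under treatment failure. AML disease control is therefore unsettled even before hydroxyurea is considered.

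**3. Following the Cycle 3 failure through the endpoints.** The subject is withdrawn. The DOR and PFS definitions do not name the resumption, Table 13 does not map it to a category, and the discontinuation list in Section 5.8 omits it. Post-treatment disease follow-up (Section 7.1.5.4.2) stops at the start of new anticancer treatment. Unless progression or relapse is recorded at or before the discontinuation visit, there may be no event.

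**4. The plan's own precision figures.** The Clopper-Pearson limits are the 0.025 quantile of Beta(x, n − x + 1) and the 0.975 quantile of Beta(x + 1, n − x). For 3/14 they give 0.047–0.508 and for 2/14 0.018–0.428, as in Table 11. All 11 rows of that table's confidence intervals reproduce to three decimals.

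**5. Size per subject.** One reclassified subject moves a rate by 1/n. Section 8.9 allows up to 14 DLT-evaluable subjects per dose level and 28 per tumor type: 1/14 = 7.1 points and 1/28 = 3.6 points. The table assumes 3 observed responders; the number exposed to hydroxyurea is also an assumption, because the documents do not give it.

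| n | Exposed responders counted as failures | ORR (95% CI) |
|---|---|---|
| 14 | 0 | 3/14 = 21.4% (4.7–50.8) |
| 14 | 1 | 2/14 = 14.3% (1.8–42.8) |
| 14 | 3 (all) | 0/14 = 0% (0–23.2) |
| 28 | 0 | 3/28 = 10.7% (2.3–28.2) |
| 28 | 1 | 2/28 = 7.1% (0.9–23.5) |

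**6. Eligibility passages side by side.** Criterion 4 and Allowed item 2 require at least 3 weeks since any anticancer therapy and make no exception for hydroxyurea. Prohibited item 1 treats hydroxyurea as an anticancer therapy and lets it run until 48 hours before treatment. Read literally, the passages conflict.

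**The case against.** Hydroxyurea is allowed only on a specific trigger and briefly, so few subjects may be affected. CR and PR are demanding: both need neutrophils above 1.0 and platelets above 100 × 10⁹/L, and PR also needs marrow blasts to fall by at least half. Nothing in the documents says that hydroxyurea produces this. A responder who needs hydroxyurea again may already have relapsed, since reappearance of blasts in the blood is relapse under Table 13, and Section 7.1.2.7.1 schedules an assessment at the discontinuation visit. DLT rate drives the RP2D, there are no hypotheses, and Section 1.0 says that no further efficacy measures will be recorded.

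All of this stands as a limit on the point. It does not supply the missing rule: the failure label still maps to no endpoint, and readings on hydroxyurea are still not distinguished.

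Four stronger readings are tempting and are not supported:
- **That the leukocytosis rate in MK-8628-001 (26/135 = 19.3%) measures the effect.** It is an adverse-event rate pooled over leukemia and other malignancies. It is not hydroxyurea use and is not limited to Cycle 1.
- **That any bias always favours activity.** For CR and PR the direction cannot be derived from the documents.
- **That the plan censors these failures.** No DOR censoring rule is written, and the PFS methods are in a supplemental SAP that is not part of these documents.
- **That each response on hydroxyurea could be re-verified later.** Scheduled assessments after Cycle 3 use blood only, which cannot verify a marrow-based response.

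**Conclusion.** The point holds as a gap between Section 5.5.1 and the AML efficacy definitions. A treatment failure declared by the protocol can leave without a DOR or PFS event, and a response or stable disease read on hydroxyurea can count as MK-8628 activity. For PFS, only the definition is shown to be silent.

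The total effect cannot be derived because the frequency of hydroxyurea use is not given. Per affected subject it is 7.1 points at n = 14 and 3.6 points at n = 28. These use the planned maxima of DLT-evaluable subjects; a smaller analysis set makes each step larger.

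The primary endpoint, the sample size and the Table 11 intervals are unaffected. The point concerns secondary and exploratory AML summaries of data already collected. It should be corrected, but it does not undermine the trial. The washout conflict is real on the page; whether sites applied it differently is not shown.

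**What to change.** Items 1 to 3 change the analysis only. Item 4 is a consistency correction.

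1. In Section 8.4.2 and the supplemental SAP, count the Cycle 3 hydroxyurea resumption that Section 5.5.1 calls treatment failure as a DOR and PFS event for AML, dated at the resumption.
2. Add one sensitivity row for AML ORR and DCR in which a response or disease control assessed only while on hydroxyurea counts as failure.
3. Reconcile the AML part of the DCR definition with Table 13, which has no stable-disease category.
4. Reconcile criterion 4 of Section 5.1.2 and Allowed item 2 of Section 5.5.1 with the 48-hour hydroxyurea allowance. Which rule should stand is for the sponsor and investigators to settle.

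The cost is a few lines of SAP text and one table row. Section 5.5.1 already requires concomitant medication in the eCRF; I assume that this record carries start and stop dates. Section 8.0 lets changes to non-confirmatory analyses go into the supplemental SAP before database lock; after lock, they would have to be labelled post hoc in the study report. The downside is that AML DCR, DOR or PFS may look slightly less favourable, as may ORR in the sensitivity row.

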### **5.6 Rescue Medications & Supportive Care**

No rescue or supportive medications are specified to be used in this trial.

#### **5.6.1 Supportive Care Guidelines**

Toxicities will be managed by the investigator according to the local standard of care, except where noted in this protocol. Supportive treatment must be reported in the concomitant medication section of the eCRF.

##### **5.6.1.1 General Guidelines for Clinically Significant Toxicities**

General guidelines regarding management and dose reduction for adverse events that are considered by the investigator to be related to study treatment are provided in Section 5.2.1.5. All adverse events should be monitored closely, with supportive care provided according to institutional standards.

### 5.6.1.2 Hepatic Laboratory Abnormalities

All trial subjects with liver test abnormalities should be followed weekly until all abnormalities return to normal or to the baseline state. For subjects with isolated total bilirubin increases  $> 2X$  ULN or  $2X$  baseline (if elevated at baseline), monitoring should be every 2 weeks until bilirubin returns to normal or to the baseline state. DILI may develop or progress even after the causative drug has been stopped. Results should be recorded on the case report form and in the database. See Section 12.8 for guidelines on the handling of these events (potential Hy's law cases).

## 5.7 Diet/Activity/Other Considerations

### 5.7.1 Diet

Subjects must avoid drinking grapefruit juice while on study, as this is a CYP3A4 inhibitor and is therefore not permitted. Subjects should otherwise maintain a normal diet, except when required to fast prior to MK-8628 administration (Section 5.2.2), or unless modifications are required to manage an AE such as diarrhea, nausea or vomiting.

### 5.7.2 Potential Phototoxicity

No phototoxicity studies have been performed in humans to date. However, as MK-8628 absorbs light in the range of 290 and 400 nm with a molar extinction coefficient (MEC) of  $> 1,000$  L/mol.cm, it is recommended that subjects avoid the sun and UV exposure until the results of phototoxicity studies are available.

